1.1 Background

The "Annual Report of the Chief Medical Officer, 2018 Health 2040 – Better Health Within Reach" draws attention to the need for a change in "the narrow approaches" used when attempting to collect data about groups or populations of people and particularly in NHS patients with multimorbidity. Most policy responses and "medical responses" are approaches designed to change the behaviour of an individual or treat clinical problems, without sufficient regard to the context in which they occur. The social determinants of health are notable by their absence. They need to be included in any medical or policy response (Ref: Office for National Statistics, 2018). Many of the health challenges facing the UK population, including rising levels of obesity, diabetes and poor mental health have multiple causes and consequences. They are both products of, and components in, complex adaptive systems. Early inclusive interventions can better slow the progress of the multiple conditions or help them regress (Ref: Davies SC, 2018).

People with long-term conditions are only seen by their Health Care Professionals (HCPs) about **3.5 hours per annum**. The rest of the time they manage with their own resources. Thus, there is the need to explore whether information on patients' vital signs and behaviours captured by wearables, monitors and other smart technologies, can identify such patients and enable them to be helped at a much earlier stage in the development of their illnesses. We believe this may enable HCPs to intervene at a much earlier stage and prevent the development of illness and associated unplanned admissions to hospital or unplanned use of primary care, mental health care or social care resources.

Meeting the needs of the growing number of people with multiple health conditions will be one of the biggest challenges facing the NHS. In 2006/07, 1 in 10 patients admitted to hospital as an emergency had 5+ long term conditions. In 2015/16, the figure was 1 in 3 patients. The number of people in England with 4+ conditions is predicted to double between 2015 and 2035 [Ref: Kingston A, 2018]. With this, there is a need to manage complex multi-morbid patients better to avoid exacerbations and emergency admissions.

Developing new models of NHS care for those with multiple conditions should be person-centred (i.e. their care should be focused on the needs of the person rather than on the needs of the service) and coordinated across primary, secondary, mental health, community and social care. Such new models of care require technology that can supports patients across various settings.

An innovative partnership between NHS England and the Health Foundation is providing quantitative evaluation to show whether local change initiatives, implemented as part of major NHS programmes, are improving care and efficiency. The NIHR Applied Research Collaborations have signalled multimorbidity as a key challenge to be tackled (Ref: NIHR, 2018).

Understanding how confident patients are about looking after their own health is essential to improve patient outcomes and clinical support. With rising demands on the health service, increasing patient self-care is a key policy focus (Ref: NHS, 2019) that can be facilitated by continuous monitoring with smart technologies. The National Health Service has committed to "give citizens the knowledge, skills and confidence to manage their own health" (Ref NHS England, 2013).

People who are more engaged in their own health tend to report better outcomes (Ref: Foot C, 2014). Interventions that improve participants self-rated confidence in complying with prescriptions and maintaining lifestyle changes have been shown to be effective in a number of long-term conditions. A

6

IRAS ID: 286225 CPMS: 44344 01/08/2020 [Proof of Concept – Smart Technology – South Lincolnshire]

PoC Protocol Version: 1.4

substantial proportion of the patient population (25%–50%) has low levels of health confidence (Ref: Hibbard JH, 2008) and this negatively impacts outcomes and experience, and increases use of emergency care. When health confidence is high, patients take more exercise, eat more healthily and avoid risks; people with diabetes report better blood sugar control. Health confidence is positively associated with patient's knowledge (health literacy) and ability to access the care they need (Ref: Wasson JH, 2009). Measures of patient confidence and engagement cover a wide domain (Ref: Coulter A, 2017), including patient-centered care (Ref: Ekman I, 2011), self-care education, patient activation and interactive health communication.

The Health Confidence Score (HCS) is a short broad generic measure for use in quality improvement and impact evaluation of the patients own perception of their health confidence. It covers health literacy and knowledge, ability to self-manage, to obtain help and involvement in shared decisions (Ref: Benson T, 2019). Such a measure could be useful both at the individual level to increase awareness of gaps in an individual's confidence, and at the aggregate level. This could be used in tandem with howRu (Ref: Benson T, 2010) which is more time responsive to change. The aggregate HCS is a meaningful summary measure and corresponds with other measure such as PWS (personal well-being score), health status (howRu) and patient experience (howRwe) in social prescribing.

At the highest level, our proposition to South Lincolnshire builds on work that Philips and Helicon Health are already doing in the UK and abroad. Our overall goals however are very ambitious from the perspectives of supporting, enabling and facilitating a series of changes. Success is the result of perfection, hard work, learning from failure, loyalty, and persistence. The architecture and approach that we have designed to support this programme is born of all the above. Our goal is to implement a system that meets the requirements but has the breadth and depth to scale to meet the greatest challenge as outlined and detailed by the 2018 Chief Medical Officer's report.

We believe that through the management of data collected in a variety of ways, we are increasingly poised to deliver what collaborators at Helicon Health have named "Precision Population Health". This enables personalised detection and protection programs to be designed and implemented with people and for people at scale. For example, this data could be collected from:

- The electronic health and care records
- From sensors in wearables recording vital signs and behavioural factors of activity and sleep
- From sensors for gait and from environmental sensors and location tracking on phones

Through the passive collection opportunities, we are looking at baseline and progression of patient reported mental and physical health status.

1.2 Summary

The source of funding for this study is NHS England. This specific funding was made available to the Proof of Concept (PoC) as a research and development project and provides executive governance via its Proof of Concept Programme Board. South Lincolnshire CCG acts as the Contracting Authority for this project. Philips Healthcare is the Prime Contractor and Helicon Health the subcontractor in the project.

The funding has been used to engage:

- Commercial Partners to deliver the PoC research projects in four areas of England (South Lincolnshire, Northamptonshire, Luton and West Essex)
- Channel 3 Consulting to manage the programme on behalf of NHS England, to assist with local project management where required, and to support NHS England in operationalising the results of the research in the NHS.

7

Each Commercial Partner was selected via an open and competitive procurement process across the EU, in-line with the requirements of the Public Contract Regulations; this approach and the procurement strategy were approved by NHS England prior to publication.

1.3 Measures in respect of Covid-19

Since the procurement was completed, the Covid-19 pandemic has become a global health threat. The public health threat it represents is the most serious seen in a respiratory virus since the 1918 HINI influenza pandemic. The current measures being taken by the UK Government to interrupt transmission have resulted in a need to adapt the research approach to change the way the research team obtain informed consent from participants and interact with participants and NHS staff throughout the study period. The intended process for obtaining informed consent is clearly described in this document along with other adaptions that were necessary to ensure safe and feasible undertaking of the study. The impact of Covid-19 will not prevent the hypothesis being tested nor will it fundamentally change the study design. The smart devices and the questionnaires will not involve human contact. The smart devices come in form of an app that can be installed from the internet. The questionnaires will be sent and completed by the patient on their smart phone, tablet or desktop. We currently are considering how we can safely use a shared Tablet in a Care home to obtain clinical information on respiratory and heart rate and BP oxygen saturation on several patients. This will involve engaging with the residential and care home staff to develop safe procedures; this will be helped by the knowledge of the Covid-19 status of both patients and staff in terms of blood antibody tests on all the staff and all the patients. We hope also that the use of PPE (Personal Protective Equipment) will be confirmed in each of the relevant homes.

In this PoC, we aim to test the hypothesis that:

"If information about patient behaviour, conditions and events, captured from wearables, monitors and other smart technologies can predict demand for services, then, providing these technologies to patients and using the data generated will enable providers to pre-empt and redirect demand or design new services"

This will be tested by deploying a series of smart technologies with sensor based wearables to study participants to collect their physiological data which will then be analysed.

We confirm that no clinical interventions will be made at a participant level during this PoC study as a result of any data collected. Our research is purely observational and will be based on historic rather than real-time data analysis. We can also confirm that all our participant data will be pseudonymised, deidentified and stored securely.

The device readings are blinded to the participants in order to avoid any feedback of the reading that may influence behaviour and ensure that the study remains non-interventional in their usual care. We will also use software based sensors that use the camera on a smart phone or iPad, and web based questionnaires to collect a richer data pool. We will additionally ingest confidential and pseudonymised Health and Social Care and Environmental data and store it all together in a cloud-based platform purpose-built for healthcare, utilising leading technologies and practices in security and privacy. Data scientists and researchers will perform data analysis and model development within the cloud-based platform using the Philips "Workbench" platform. This provides a collaborative development environment with tools that manage the end-to-end process of analytics, analytics asset creation, deployment and support.

8

IRAS ID: 286225 CPMS: 44344 01/08/2020 [Proof of Concept – Smart Technology – South Lincolnshire] PoC Protocol Version: 1.4 Suitable potential participants will be identified by their GP based on set inclusion and exclusion criteria provided by the research team. Participants will either be living in their own residence, in a residential or nursing care home. Informed consent will then be sought according to the recruitment process described in section 3 of this document.

To find the suitable participants the research team will apply **Diagnostic Stratification Technique** algorithms based on Machine Learning, Neural Networks and Artificial Intelligence (AI) to analyse clinical patterns from de-identified patients. These patients' details will already be stored in the NHS in databases such as Hospital Episode Statistics (HES) which is a data warehouse containing details of:

- All admissions
- Outpatient activity
- A & E attendances
- GP data
- Social Care records

By these means we will find pseudonymised NHS patients who have more than 3 long term conditions (LTC) which will be aligned with the capabilities of data collection of the smart technologies to be used during the study. Using this selection process, the research team aims to identify 700 pseudonymised NHS patients to be approached to participate in the study.

Each participant who consents to take part in the study will be issued with one or more of the smart technologies or sensor-based wearables which will not disturb their day to day activities. The allocation of these technologies is described in subsequent sections of this document. For a period of approximately six months we will record their vital signs and other readings in a secure cloud environment. Our data scientists and researchers will then be able to perform analyses and model development. This will conclude the first phase of the research (Phase 1).

In order to develop use cases, patient pathways and service recommendations, which may be largely based on those data collected, we will work with the CSU to ensure information governance permissions are in place to carry this out (Phase 2). We intend to make assessments of the likely qualitative and economic benefits of the predictive system based on the data collected. These will be tested through data quality evaluation, model selection, training data categorisation, learning algorithm(s), sensitivity and specificity analyses to help determine the confidence of the predictive systems (Ref: Longstaff 2010). The benefits can accrue in several parts of the "services". We will attempt to define the proportions in each.

2. Study Purpose

2.1 Testing the hypothesis

The principal research question is to test the hypothesis:

"If information about patient behaviour, conditions and events, captured from wearables and other smart technologies can predict demand for services, then providing these technologies to patients and using the data generated, will enable providers to pre-empt and redirect demand or design new services."

9

The hypothesis will be tested by deploying smart technologies with sensor-based wearables, software sensors using the camera on a smart phone or tablet, and web based questionnaires to study data from the participants.

We will further include pseudonymised Health and Social Care and Environmental data and store it together in a cloud-based platform purpose-built for healthcare, utilising leading technologies and practices in security and privacy.

Data scientists and researchers will perform data analysis and model development within the collaborative development environment with tools that manage the end-to-end process of analytics, analytics asset creation, deployment and support.

We will also be testing whether the use of multiple smart technologies of this nature, is acceptable to patients, easy to use and comfortable.

The analytics will seek to understand whether the use of such technologies and the data gathered from them, can indeed provide useful information in predicting adverse healthcare events and therefore inform the transformation of health services to make interventions sooner to achieve better outcomes.

3. Study design

A high-level outline of the research study design is illustrated below in Table A.

Table A: High Level Outline of Research Design

Our research is observational only and based on historic data. No clinical interventions to a patient's usual care will be made during the study as a result of any data collected. All the data collected will be pseudonymised and will not be monitored or analysed in real time.

The participant will not be able to see the physiological health readings recorded by the smart technologies and so will not have new information about their health which might prompt them to contact their GP or other healthcare services. Therefore, the clinical care of the patient will continue as normal by their GP and/or other health care professionals. This will be fully explained to participants during the recruitment and consenting process.

10

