Commented [**CP5**]: Can we say – "Optima will then post devices and instructions on how to use them to participants. As soon as the participant receives their devices they will be able to start using them to take health measurements straight away. If a participant has any difficulty in using their devices, they will be able to call Optima Systems for support and guidance".

IRAS ID: 286225 CPMS: 44344 01/08/2020 [Proof of Concept – Smart Technology – South Lincolnshire] PoC Protocol Version: 1.4 15

Device / App name	Physiological measurement	Characteristics of	device / app	Participants
LifeLight	 Respiratory & heart rate, BP & pO₂ 	Digital camera on iPad		As many as possible – proportion shared in Care homes – readings daily
Thermometer	Temperature	Hand held the	rmometer	All participants for 6 days/week
FibriCheck	• ECG – (FIBRICHECK)	Visual Plethysn	nography	300 participants – daily readings
Device / App name	Behavioural	measurements		
GENEactive	 Activity inter 	Activity intensity / duration &		500 participants
Band	frequency/ sleep quality			Daily readings
QuestLink	 Mental, social and physical health status and progression. Measures of patient self-confidence (HCS) and Health Status (howRU) 		All participan	ts - on average twice weekly

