QuestLink enables surveys to be automatically scheduled and distributed to the participants devices. This will include measures of participants self-confidence (Health Confidence Score) and Health Status (howRU) for participants with multimorbidity; mental health, social and physical health status, and progression; current medication and changes and others. It will also include the use of a handheld thermometer to enter the temperature 6 times a week.

TABLE B – Measurement details, devices and details of device/app

Physiological measurement	Device / App name	Characteristics of device / app
Respiratory rate	LifeLight	Digital camera on iPad
Oxygen saturation	LifeLight	Digital camera on iPad
Blood pressure	LifeLight	Digital camera on iPad
Temperature	Thermometer	Hand held thermometer
• ECG – (FIBRICHECK)	FibriCheck	Visual Plethysmography

Behavioural measurements	Device / App name	Characteristics of device / app
Activity intensity / duration & frequency	ActivInsights Band	Wearable Band
 Sleep / Circadian cycle / Sleep time and duration & quality 	ActivInsights Band	Wearable Band
Acceleration monitor for bone health	ActivInsights Band	Wearable Band

18

IRAS ID: 286225 CPMS: 44344 01/08/2020 [Proof of Concept – Smart Technology – South Lincolnshire]

PoC Protocol Version: 1.4

Rehabilitation balance and safety in falls patients	ActivInsights Band	Wearable Band
• Mental, social and physical health status and progression. Measures of patient self-confidence (HCS) and Health Status (howRU)	QuestLink	Cloud based Response to questions – personalised and automatically scheduled and distributed to participant devices

Environmental & Social determinants of health		
Air quality - pollutants	Sensor Related to postal code	Static – accessed from "public sites"
Postcode or GP Postcode –	First digits of postcode	Static data
Lincolnshire Research Observatory (LRO)	Index of Multiple Static – accessed from "public sites Deprivation (IMD)	

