5.1.3 The start of the PoC Study

23

IRAS ID: 286225	[Proof of Concept – Smart Technology – South Lincolnshire]
CPMS: 44344	PoC Protocol Version: 1.4
01/08/2020	

The start of the PoC study will, in the first 2-3 weeks, entail the recording physiological and behavioural data on pseudonymised participants and will serve to calibrate the expected measurements of each individual participant. Once the formal cohorts have been created and the individuals are supplied with and using the appropriate equipment, data scientists from Helicon and i5 Health will use the unique research platform with six months of sensor based data. During data analysis and model development, various hypotheses will be tested against the data.

The use of QuestLink, an electronic questionnaire will enable us to collect mental, social and physical health status and its progression on individual participants on a regular basis. It can also serve as a messaging service to collect such information from the participants as a list of their current medication, wellbeing or their minor illnesses. It will enable the use of measures, relevant to patients with multimorbidity, of patient self-confidence (HCS) and Health Status (howRU).

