5.4 Study Steering Group

A Study Steering (SSG) will oversee the organisation, the data quality and the output of the study. The steering group will oversee the data flows and management. To aid them they will use make use

25

of a monitoring device that ensures the correct and consistent correlation of the participant's PoC study number with the ID number of the wearable, sensor and monitor; and will generate a warning of any inconsistency.

Table F below illustrates the flow of data in the analytic phases of the PoC Smart Technology DataStudy Trial:

Phase 1 with the flow from the physiological and behavioural data mainly but with QuestLink data also

- Phase 2 with the additional data from the clinical health and social care data, together with Air quality
- Predict events Phase 1 with the "predict events" data
- Budget Phase 1 with the budget data linked to the relevant phases and support the development of the transformation report

Commented [CP8]: Needs rewording to fit with new study stages Data Collection Analysis Results

6. Ethical Considerations

Due to Covid-19, consenting processes have been adapted to ensure that consent is undertaken remotely. We considered adopting electronic means but have now decided to adopt a modified paper based system which has produced good results and with which the LCRN are familiar.

The research team will provide GP Practices with the following "participant facing documents" to use in recruitment activities with their own patients:

1. Participant Invitation Letter

26

IRAS ID: 286225	[Proof of Concept – Smart Technology – South Lincolnshire]
CPMS: 44344	PoC Protocol Version: 1.4
01/08/2020	

This will give a brief summary of the study and instructions on how to either accept or decline the invitation.

2. Participant Information Sheet (PIS)

This will provide a more detailed explanation of the study including what the participant will need to do, why we are undertaking the study, how they can withdraw from participation etc. a copy of the PIS has been submitted with this application.

3. Study Consent Form

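### The hypothesis about wearables and smart technologies is to be tested on sensors and questionnaires together, so a combined result alone would not show what the sensors add to self-report

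*Protocol*

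**What the plan says.** - **Hypothesis (section 2.1).** It concerns information "captured from wearables and other smart technologies can predict demand for services", and goes on to what would follow from providing those technologies to patients.
- **Test, as given in 2.1.** Sensor-based wearables, plus "software sensors using the camera on a smart phone or tablet, and web based questionnaires to study data from the participants".
- **Test, as given in 1.3.** Smart technologies with sensor-based wearables are deployed to collect physiological data, which are then analysed. Questionnaires come in afterwards, as "web based questionnaires to collect a richer data pool".
- **Staging (section 5.4).** "Phase 1 with the flow from the physiological and behavioural data mainly but with QuestLink data also". Clinical, social care and air quality data are added in Phase 2.
- **Model choice (section 5.2, stage (d)).** Several models and topologies are trained to find the combination that performs best. No comparison between data sources is named.
- **QuestLink content.** Section 4.1 lists health confidence, health status and "current medication and changes and others", and says the hand-held thermometer reading is entered through it. Section 5.1.3 says it can also be used to collect "a list of their current medication, wellbeing or their minor illnesses". The device table in 3.4.1 gives QuestLink to all participants "on average twice weekly".
- **Demand data (section 4.2).** GP and other attendances, hospital activity and prescribing come from NHS sources.

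**The concern.** The two descriptions of the test do not have the same inputs. Questionnaire answers are not physiological data, so the description in 1.3 leaves them out and the one in 2.1 puts them in. The staging in 5.4 separates NHS and environmental data from the sensors but does not separate self-report from the sensors. A rule that seeks the best-predicting combination will take accuracy from whichever source supplies it.

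This matters because the hypothesis leads to a decision about providing technology. Section 4 rests the case for scaling up on data gathered as passively as possible, and filling in a questionnaire is not passive. A person who reports feeling worse, a minor illness or a change of medication may be close to a service contact, or may just have had one. If such answers carried the prediction, a good combined figure could be read as support for bands and camera apps that had contributed little. If the sensors did contribute, the same figure would not show that either.

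**Working it through.** **1. Inputs to the test, side by side**

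| Place | Sensors | Questionnaires |
|---|---|---|
| 1.3, how the hypothesis is tested | yes (physiological data) | not named in that sentence; added later to enrich the data |
| 2.1, how the hypothesis is tested | yes | yes |
| 5.4, Phase 1 | yes, mainly | yes |
| 5.2(d), selection | best combination | best combination |

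None of these places gives a result for sensors alone, or with and without QuestLink.

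**2. What a combined figure can show**

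The protocol states no AUC, effect size or event rate, so there is no figure to reproduce. All AUC values below are assumed, for illustration only.

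Take a sensor score and a questionnaire score that are independent and normal with equal variances in people with and without an event. Then

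AUC = Φ(d/√2), so d = √2 · Φ⁻¹(AUC), and d²(combined) = d²(sensor) + d²(questionnaire).

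*One case.* A sensor AUC of 0.55 gives d = 0.178. A questionnaire AUC of 0.75 gives d = 0.954. The combined d is √(0.178² + 0.954²) = 0.970, so the combined AUC is Φ(0.970/√2) = 0.754. The gain over the questionnaire alone is 0.754 − 0.750 = 0.004.

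*In reverse.* Fix the combined AUC at 0.75 (d = 0.954) and vary the sensors' share of d²:

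| Sensor share of d² | Sensors-only AUC | Questionnaire-only AUC |
|---|---|---|
| 0 | 0.500 | 0.750 |
| 0.25 | 0.632 | 0.720 |
| 0.50 | 0.683 | 0.683 |
| 0.75 | 0.720 | 0.632 |
| 1 | 0.750 | 0.500 |

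For a combined AUC of 0.70 the sensors-only value can lie anywhere from 0.50 to 0.70, and for 0.80 from 0.50 to 0.80. The combined figure does not fix the sensors' part. In practice the two scores would probably be correlated. The split would then differ, and the sensors-only AUC and the gain over the questionnaire would answer different questions, which is why both are needed.

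**3. Can the sources be separated?**

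Yes. Section 4.2 lists device data and questionnaire results as separate sources, and section 5.2 describes linked data sets joined by a key. One item has no clear place: temperature is listed as a physiological measurement in Table B but is typed in through QuestLink (4.1).

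**4. Time order**

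Demand is recorded by the NHS and not by QuestLink, so an answer is a predictor and not the outcome itself. An answer given after a consultation can still reflect that consultation. Section 4.2 also lists prescribing changes among the NHS data, so one medication change could appear both there and in a questionnaire. The protocol does not order answers relative to the contact being predicted.

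**The case against.** The strongest reply is that QuestLink is itself one of the technologies. It stands in the device and app table in 3.4.1, in Table B, and under the 4.1 heading for the chosen wearables, sensors and monitors. The hypothesis also covers conditions and events as well as behaviour. The sentence "The smart devices and the questionnaires will not involve human contact" names devices and questionnaires separately, but it concerns infection risk and is weak evidence about the hypothesis. The 1.3 description of the test is loose too: read literally, it would also omit the band's activity and sleep data, which Table B calls behavioural. All of this stands. It means that the scope of the hypothesis is unsettled, and it does not make a combined figure informative about the sensors.

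A second reply is that 5.4 describes data flow and not a model, that a draft comment there marks text for rewording, and that comparisons of feature sets and predictor windows often belong in an SAP, which is not shown here. This also stands in part. The absence of such detail is not the point. The point is that the protocol states the test in two ways and names best prediction as its only basis for choosing between models.

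A reader might infer three stronger things that the protocol does not support:

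- **That the study cannot separate sensors from self-report.** It can, because the data sets are separate and linkable.
- **That participants report illness and medication changes twice a week, so almost every contact is soon followed by a report.** The twice-weekly entry in 3.4.1 names health status, health confidence and howRU. Section 4.2 puts medication questions at unspecified intervals, and 5.1.3 mentions minor illness only as something QuestLink can collect.
- **That the outcome leaks into the predictors.** This is possible, but nothing says that answers given after a contact will be used to predict it.

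**Conclusion.** The point holds in limited form. Sections 1.3 and 2.1 give different inputs for the test of the principal hypothesis. Section 5.4 keeps self-report in the same stage as the sensors, and 5.2(d) looks for the best combination. A combined result alone would therefore not show whether the sensors add anything to self-reported health. The study remains able to answer the question if the comparison is fixed in advance. The size of the problem cannot be derived from the protocol. The AUC figures rest on assumed values, normality and independence, and show only that the sensors' part is not identified. That self-report would dominate is a possibility and not a finding. The correction should be made before results are seen, because it changes what the study can conclude about wearables.

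**What to change.** - **Section 2.1 (with 1.3).** Reconcile the two descriptions of the test, and state whether QuestLink is part of the hypothesis or an additional source.
- **Sections 5.2 and 5.4.** At whichever stage demand is modelled, report three models on the same participants and the same data split: sensors only, QuestLink only, and combined. Using the same participants matters because the table in 3.4.1 gives QuestLink to everyone but FibriCheck to 300.
- **Decision rule.** Judge the wearable and sensor claim on the sensors-only result and on the gain of combined over QuestLink-only. The combined figure can still be reported as the performance of the whole system.
- **Temperature.** State in which set the hand-entered reading falls.
- **Timing.** Use as predictors only QuestLink answers dated before the service contact being predicted.

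The cost is two further model fits on data already collected, and possibly a less favourable figure for the sensors. No new data, visits or devices are needed.
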